9.1. Efficacy Assessments

9.1.1. Primary Efficacy Assessments

The primary efficacy assessment is to determine the time to disease flare from Week 12 to the end of the DBW period. Disease flare is defined as a worsening of $\geq 30\%$ in at least 3 of the 6 PedACR core criteria for JIA and an improvement of $\geq 30\%$ in no more than 1 of the criteria from the patient's condition at the conclusion of the OLLI period. If either the number of joints with active arthritis or the number of joints with limitation of motion are used in the calculation of flare for a study visit, then a minimum worsening of at least 2 active joints or 2 joints with limitation of motion must be evident. If either the Physician's Global Assessment of Disease Activity or the Parent's Global Assessment of Well-Being are used in the calculation of flare for a study visit, then a minimum worsening on a visual analogue scale (as defined in the SAP) must be evident (Brunner et al. 2002, Ruperto et al. 2008). In order to diagnose PedACR30 response at Week 12 and "flare" during the DBW period on-site in a timely manner, ESR is used as the acute phase reactant in PedACR core criteria.

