10.3.3. Efficacy Analyses

10.3.3.1. Primary Analyses

The primary efficacy endpoint is time to disease flare (flare defined as worsening of $\geq 30\%$ in at least 3 of the 6 PedACR core criteria for JIA and an improvement of $\geq 30\%$ in no more than 1 of the criteria) during the DBW period for the DBW population. If either the number of joints with active arthritis or the number of joints with limitation of motion are used in the calculation of flare for a study visit, then a minimum worsening of at least 2 active joints or 2 joints with limitation of motion must be present. An active joint is defined as a joint with swelling or, in the absence of swelling, limitation of motion accompanied by pain on motion and/or tenderness. If either the Physician's Global Assessment of Disease Activity or the Parent's Global Assessment of Well-Being are used in the calculation of flare for a study visit, then a minimum worsening (as defined in the SAP) on the visual analogue scale (VAS) must be present. If ESR or CRP is used in the definition of "flare" and counts towards worsening, then the second value for ESR or CRP used in the calculation must be above the upper limit of normal for ESR (>20 mm/hour) or CRP. In JAHV, for primary analysis, disease flare definition will only use ESR.

The 6 PedACR core criteria (Gianni et al. 1997) includes:

- Number of active joints (defined as a joint that is swollen or in the absence of swelling has loss of passive motion accompanied by either pain on motion or joint tenderness) in 73 joints
- Number of joints with limited range of motion in 69 joints
- Physician's Global Assessment of Disease Activity
- Parent's Global Assessment of Well-Being
- Physical function as assessed by the CHAQ
- Acute-phase reactant (hsCRP and ESR)

Patients who discontinue the DBW period without experiencing a flare will have their data censored. A stratified logrank test across all JIA subtypes will be used as the primary analysis method. Survival curves will be estimated using the Kaplan–Meier method for all "time-to" variables in the DBW period.

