disease flare	Worsening of 30% or more in at least 3 of the 6 PedACR core criteria for JIA and an improvement of 30% or more in no more than 1 of the criteria from the patient's condition at the conclusion of the OLLI period
disease response	Improvement of 30% or more in at least 3 of 6 PedACR core-response variables without a worsening of greater than 30% in more than 1 variable
DMARD	disease-modifying antirheumatic drug
DMC	data monitoring committee
DNA	deoxyribonucleic acid
ECG	electrocardiogram
eCRF	electronic case report form
eGFR	estimated glomerular filtration rate
enroll	The act of assigning a patient to a treatment. Patients who are enrolled in the study are those who have been assigned to a treatment.
enter	Patients entered into a study are those who sign the informed consent form directly or through their legally acceptable representatives.
EQ-5D-Y	European Quality of Life-5 Dimensions–Youth version
ERA	enthesitis-related juvenile idiopathic arthritis
ETV	early termination visit
EULAR	European League Against Rheumatism
GCP	good clinical practice

Term	Definition
hBsAb	hepatitis B surface antibody
hBsAg	hepatitis B virus surface antigen
HBV	hepatitis B virus
HCV	hepatitis C virus
HIV	human immunodeficiency virus
HRQOL	health-related quality of life
hsCRP	high-sensitivity C-reactive protein
IB	Investigator's Brochure
ICF	informed consent form
ICH	International Council for Harmonisation
Ig	immunoglobulin
IGF-1	insulin-like growth factor-1
IGFBP-3	insulin-like growth factor-binding protein-3
IL	interleukin
ILAR	International League of Associations for Rheumatology
Informed consent	A process by which a patient voluntarily confirms his or her willingness to participate in a particular study, after having been informed of all aspects of the study that are relevant to the patient's decision to participate. Informed consent is documented by means of a written, signed and dated informed consent form.
INR	international normalized ratio
interim analysis	An interim analysis is an analysis of clinical study data, separated into treatment groups, that is conducted before the final reporting database is created/locked.

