6.10. Efficacy Analyses

6.10.1. Primary Outcome and Methodology

Time to disease flare (time is measured by week) is used as the primary outcome, which will be calculated as follows:

$$(\text{Date of Flare} - \text{Date of Randomization in the DBW} + 1)/7$$

The flare-ESR is calculated based on the flare definition and PedACR core criteria defined in Section 4.1, Table JAHV.4.1, Table JAHV.4.2, and Table JAHV.6.6, and uses ESR as acute-phase reactant. The detail of disease flare calculation is documented in separate disease flare and PedACR response calculation algorithm document. Patients completing the DBW period without flare will be censored at the date of completion (ie, the date of the last visit in the period).

Patients who discontinued treatment early in the DBW period without flare will be censored at the treatment discontinuation date.

The primary analysis of the study is to test for the hypotheses that baricitinib is superior to placebo in prolonging the time to disease flare in PedACR 30 responders from Week 12 to Week 44 using the DBW population.

A stratified logrank test will be used as the primary analysis method, in which the log-rank test will be stratified on the JIA categories:

- polyarticular and extended oligoarticular[combined]
- enthesitis-related JIA and JPsA[combined]

The p-value and median time to flare (if applicable) by treatment group will be reported. Treatment comparisons may also be analyzed using a Cox proportional hazards model adjusted for stratification variables. The hazard ratio with 95% CIs will be reported. The Kaplan-Meier product limit method will be used to estimate the survival curves for time-to flare. Time-to flare will also be summarized graphically by treatment group using Kaplan-Meier techniques.

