6.10.2. Secondary Efficacy Analyses

Secondary efficacy and health outcomes analyses ([Table JAHV.6.4](#)) will be based on treatment periods with the respective population at each visit. The analysis method is described in [Table JAHV.6.5](#). There will be no adjustment for multiple comparisons.

Table JAHV.6.4. Description and Derivation of Primary, Secondary Efficacy Endpoints and Health Outcomes

Measure	Description	Variable	Derivation/Comment	Imputation Approach if with Missing Components
Disease flare	
Disease flare is defined as a worsening of $\geq 30\%$ in at least 3 of the 6 PedACR core criteria for JIA and an improvement of $\geq 30\%$ in no more than 1 of the criteria from the patient's condition at randomization baseline. In disease flare-ESR, ESR measure is used as acute-phase reactant in the core criteria.
 
 • If either the number of joints with active arthritis or the number of joints with limitation of motion are used in the calculation of flare for a study visit, then a minimum worsening of at least 2 active joints or 2 joints with limitation of motion must be present. • An active joint is defined as a joint with swelling or, in the absence of swelling, limitation of motion accompanied by pain on motion and/or tenderness. • If either the Physician's Global Assessment of Disease Activity or the Parent's Global Assessment of Well-Being are used in the calculation of flare for a study visit, then a minimum worsening of at least 20 mm in 0-100 mm visual analogue scale (VAS) must be present. • If ESR is used in the definition of "flare" and counts towards worsening, then the second value for ESR used in the calculation must be above the upper limit of normal for ESR (>20 mm/hour). 	Time to disease flare	
The details of disease flare calculation are documented in separate disease flare and PedACR response calculation algorithm document.
 
Calculation: Date of disease flare-ESR minus date of randomization+1
	
Component is missing if baseline or postbaseline value is missing. LOCF will be applied for post baseline missing values. If more than 3 components are missing, there will not be sufficient information; thus, the patient will be considered as a non-flare patient.

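### Protocol 9.1.1 states the on-site flare definition without the ESR >20 mm/hour condition used in the primary analysis, so a child could exit as a flare and then be censored as flare-free

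*Protocol*

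**What the plan says.** Protocol 9.1.1 gives the 30% rule and the two-joint minimum. For the two global assessments it adds a minimum by reference: "then a minimum worsening on a visual analogue scale (as defined in the SAP) must be evident". It then says that, so that flare can be diagnosed "during the DBW period on-site in a timely manner, ESR is used as the acute phase reactant in PedACR core criteria". No ESR threshold follows.

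Section 5.1.4 also says that ESR is used so that flare can be called on site in real time, and gives only the 30% rule. Table JAHV.4 does the same for the endpoint. Appendix 1 defines flare as "Worsening of 30% or more in at least 3 of the 6 PedACR core criteria for JIA", with the limit on improvement and no minimum conditions.

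The Synopsis (Treatment Arms and Duration) and Section 10.3.3.1 go further: if ESR or CRP counts towards worsening, the second value "must be above the upper limit of normal for ESR (>20 mm/hour) or CRP". Section 10.3.3.1 adds: "In JAHV, for primary analysis, disease flare definition will only use ESR". SAP Table JAHV.6.4 repeats the ESR condition and sets the size of the global minimum: "then a minimum worsening of at least 20 mm in 0-100 mm visual analogue scale (VAS) must be present".

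Protocol 5.4 takes a child out of the study at the first flare. SAP 6.10.1 then says: "Patients who discontinued treatment early in the DBW period without flare will be censored at the treatment discontinuation date". The details of the flare calculation are left to a separate algorithm document.

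**The concern.** The primary endpoint is decided twice. The site calls flare at the visit, and that call ends follow-up. The SAP later derives flare from the recorded components. If the two use different conditions, a child can be removed as a flare and then carry no event in the analysis. Such a child is censored because of worsening, so the censoring is related to outcome, which the log-rank test assumes it is not. On the planned flare rates, more of these children would be on placebo. No passage says how a site-called flare that fails the derived definition is handled, other than through the general censoring rule.

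**Working it through.** **1. The definitions side by side.**

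| Place | ESR >20 mm/hour | Two-joint minimum | VAS minimum |
|---|---|---|---|
| Protocol Synopsis, Treatment Arms and Duration | yes | yes | by reference to SAP |
| Protocol Table JAHV.4 | no | no | no |
| Protocol 5.1.4 | no | no | no |
| Protocol 9.1.1 | no | yes | by reference to SAP |
| Protocol 10.3.3.1 | yes | yes | by reference to SAP |
| Protocol Appendix 1 | no | no | no |
| SAP Table JAHV.6.4 | yes | yes | 20 mm on 0-100 mm |

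The ESR column is a true difference. The VAS column is not: 9.1.1 imports whatever the SAP sets. What is missing from the protocol is the figure of 20 mm. Nor is that figure mapped to the physician's scale, which runs from 0 to 10 in steps of 0.5 (Protocol 9.1.2.7). A proportional reading would make it 2.0 points, but neither document says so.

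**2. A child on whom the definitions disagree** (illustrative values, Visit 9 to a later visit).
- Active joints 2 to 4: +100%, and +2 joints, so the joint minimum is met.
- CHAQ 0.50 to 0.75: +50%.
- ESR 8 to 12 mm/hour: +50%, still not above 20.
- The other three components are unchanged.

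Under 9.1.1 as written, 3 of 6 criteria have worsened and none has improved: flare, and exit. Under the Synopsis, 10.3.3.1 and SAP Table JAHV.6.4 the ESR rise does not count, so 2 of 6 have worsened: no flare, and censoring at treatment discontinuation.

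**3. The planned power.** Inputs from Protocol 10.1: 64 per arm, flare 35% v 60%, two-sided alpha 0.05, dropout at most 10%.
- HR = ln(0.65)/ln(0.40) = 0.470.
- Expected flares = 64 × 0.35 + 64 × 0.60 = 22.4 + 38.4 = 60.8; with 10% loss, 60.8 × 0.9 = 54.7.
- Schoenfeld power = Φ(√d × |ln HR|/2 − 1.96). With d = 54.7 this is 79.7%. The stated figure of approximately 80% reproduces. Freedman's formula gives 80.2% at 60.8 events without dropout.

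**4. Illustration of loss.** Suppose a share m of flares in each arm becomes censored exits, with the hazard ratio unchanged, so that d = 54.7 × (1 − m). The documents give no value for m; the range is assumed.

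| m | Events | Power (Schoenfeld, 10% dropout) |
|---|---|---|
| 0 | 54.7 | 79.7% |
| 5% | 52.0 | 77.7% |
| 10% | 49.2 | 75.4% |
| 20% | 43.8 | 70.4% |

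At m = 10%, before dropout, about 38.4 × 0.1 = 3.8 placebo and 22.4 × 0.1 = 2.2 baricitinib flares would be reclassified. Freedman's formula without dropout falls in parallel: 80.2%, 78.2%, 76.0%, 71.0%.

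**The case against.** The strongest reply is that there is one intended definition and 9.1.1 merely repeats it incompletely. The protocol itself states the ESR condition twice, and in the Synopsis it is not confined to the analysis. SAP 6.1.3 ends the double-blind period at flare as defined in Table JAHV.6.4, which contains the condition. Nothing says that sites read 9.1.1 alone. Section 5.1.4 points to Section 9 for the core criteria and the dual-assessor procedures, not for the flare definition, and Appendix 1 is plainly a shortened glossary entry. The algorithm document, or the Trial Manager report that must be reviewed before dispensing (footnote j, Table JAHV.2), may already align the two calls.

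Most of this stands. A reader might infer that the protocol has no ESR rule, or that the VAS minimum conflicts between the documents; neither is so. What remains is that 9.1.1, the fullest account of on-site diagnosis, is looser than the analysis definition. SAP 6.1.3 shows what the analysts intend, not what a site does at the visit. The algorithm is cited only for the SAP calculation, and the report's content is not described. If either closes the gap, the plan does not say so.

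**Conclusion.** The flare definition is stated inconsistently, and the stated censoring rule would produce outcome-related censoring for any child whose site call and derived status differ. That much follows from the texts.

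The frequency does not. A reader might infer that children are in fact being counted as flare-free when they flare, or that the trial loses a known amount of power. The documents support neither. The power figures of about 78%, 75% and 70% rest on an assumed mismatch of 5%, 10% and 20%, equal in both arms, with each discordant exit replacing a flare that would have been derived. A child whose third criterion was a within-normal ESR rise might never have met the derived definition, and then no event is lost. Because the illustration holds the hazard ratio fixed, it shows lost information only and does not measure bias.

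The sample-size statement is not in dispute. Nor does this point say which condition ought to govern a child's exit. It is worth correcting because it touches the primary endpoint and costs little.

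**What to change.** **Protocol and SAP wording.** Reconcile the flare definition across the Synopsis, Table JAHV.4, Sections 5.1.4, 9.1.1 and 10.3.3.1, Appendix 1 and SAP Table JAHV.6.4, so that the on-site and analysis definitions are the same. The sponsor decides which rule governs exit. Give the VAS minimum in the protocol as well as the SAP, and state how it applies to the physician's 0-10 scale. If the algorithm document or the Trial Manager report already aligns the two calls, say so.

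**SAP 6.10.1.** Tabulate by arm the exits recorded as flare that do not meet the derived definition. Add a sensitivity log-rank test, stratified as in the primary analysis, that counts them as events on the exit date.

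**Cost.** Wording changes, one table and one sensitivity analysis. No new data: reasons for discontinuation are already to be recorded and summarised (Protocol 8.2 and 10.3.2.1, SAP 6.6). If there are no discordant exits, the table shows zeros and the question is closed.

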9.1.2. Secondary Efficacy Assessments

Secondary endpoints (assessed at each visit, except Visit 3) are as follows:

- Proportion of patients with disease flare during the DBW period.
- Changes from baseline in each of the 6 individual components of the PedACR core set variables during the OLLI period and during the DBW period
- PedACR30/50/70/90/100 response rates during the OLLI period and during the DBW period.
- Changes from baseline in the Physical Summary Score (PhS) and Psychosocial Summary Score (PsS) of the Child Health Questionnaire-Parent Form 50 (CHQ-PF50) during the OLLI period and during the DBW period.
- Changes from baseline in caregiver burden as measured by the Parental Impact-Time and Parental Impact-Emotion scales of the CHQ-PF50 during the OLLI period and during the DBW period.
- Proportion of patients with inactive disease (as defined by Wallace et al. 2011) during the OLLI period and during the DBW period.
- Proportion of patients in remission (as defined by Wallace et al. 2012) during the DBW period.
- Proportion of patients with minimal disease activity (as defined by Consolaro et al. 2012) during the OLLI period and during the DBW period.
- Change from baseline in JADAS-27 during the OLLI period and during the DBW period.
- Changes from baseline in arthritis-related pain severity as measured by the CHAQ pain severity VAS item during the OLLI period and during the DBW period.
- In patients with JPsA:
 - Change from baseline in PASI score during the OLLI period and during the DBW period.
- In patients with JPsA or ERA:

- Change from baseline in SPARCC enthesitis index during the OLLI period and during the DBW period.
- Change from baseline in the JSpADA during the OLLI period and during the DBW period.
- Change in immunoglobulin levels and peripheral blood immunophenotyping (including T and B cells, T cell subsets, and NK cells) from baseline during the OLLI period and during the DBW period.
- Change of IgG titers from pre-vaccination to 4 weeks and 12 weeks post-vaccination in patients eligible for vaccination with tDaP and/or pneumococcal conjugate vaccine according to local guidelines.
- Assessment of tablet or oral suspension product acceptability and palatability at baseline and Week 12.
- Safety variables
 - AEs including SAEs
 - Permanent discontinuation of investigational product
 - Temporary interruption of investigational product

9.1.2.1. PedACR30/50/70/90/100 Assessments

The PedACR30 consists of the 6 core criteria listed below. The definition of improvement is at least 30% improvement from baseline in 3 of any 6 variables in the core set, with no more than 1 of the remaining variables worsening by >30%. Pediatric ACR50 and ACR70 improvement criteria are defined as above with improvements of 50% and 70%, respectively.

- Number of active joints (defined as a joint that is swollen or in the absence of swelling has loss of passive motion accompanied by either pain on motion or joint tenderness) in 73 joints
- Number of joints with limited range of motion in 69 joints
- Physician's Global Assessment of Disease Activity (21-circle visual analogue scale [VAS]) (Section 9.1.2.7)
- Parent's Global Assessment of Well-Being (Section 9.1.5)
- Physical function as assessed by the Childhood Health Assessment Questionnaire (CHAQ) (Section 9.1.5)
- Acute-phase reactant (hsCRP and ESR)

ACR50, ACR70, ACR90, and ACR100 responses are efficacy measures that are calculated as improvements of at least 50%, 70%, 90% and 100%, respectively, in the PedACR Core Set values listed above.

9.1.2.2. Juvenile Arthritis Disease Activity Score-27

The JADAS-27 score is a validated composite disease activity measure for JIA (Consolaro et al. 2012). Recently, the scoring system was adapted to use the 27-joint count (Bazso et al. 2009), and hsCRP or ESR for the inflammatory marker component (Nordal et al. 2012). The JADAS-27 includes the following joints: cervical spine, elbows, wrists, metacarpophalangeal joints (from first to third), proximal interphalangeal joints, hips, knees, and ankles.

JADAS-27 score will be determined based on 4 components:

- Physician's Global Assessment of Disease Activity (Section 9.1.2.7)
- Parent's Global Assessment of Well-Being (from CHAQ; Section 9.1.5)
- Number of joints with active disease (27-joint assessment)
- hsCRP or ESR as applicable

9.1.2.3. Disease Activity

Minimal Disease Activity

Minimal disease activity is calculated based on the scores from the Physician's Global Assessment of Disease Activity (Section 9.1.2.7), Parent's Global Assessment of Well-Being (Section 9.1.5), and the number of swollen joints as described in the SAP and Consolaro et al. 2012.

Inactive Disease

Inactive disease is indicated by the presence of all of the following (Wallace et al. 2011):

- No joints with active arthritis based on JADAS-27 (Section 9.1.2.1)
- No fever, rash, serositis, splenomegaly, hepatomegaly, or generalized lymphadenopathy attributable to JIA as assessed by the investigator
- No active uveitis as assessed by the investigator
- Normal erythrocyte (ESR) or hsCRP (i.e., within normal limits in the local laboratory or, if elevated, not attributable to JIA)
- Physician's Global Assessment of Disease Activity indicating no active disease (best possible score on scale [0]) (Section 9.1.5)
- Duration of morning stiffness ≤ 15 minutes

Remission

Remission is defined as inactive disease for at least 24 consecutive weeks (Wallace et al. 2012).

9.1.2.4. Psoriasis Area and Severity Index

The PASI combines assessments of the extent of body-surface involvement in 4 anatomical regions (head, trunk, arms, and legs). It also assesses the severity of erythema (redness), plaque induration/infiltration (thickness), and desquamation (scaling) in each region, yielding an overall score of 0 (no psoriasis) to 72 (most severe disease [Fredriksson and Pettersson 1978; Mease 2011]).

The head, upper extremities, lower extremities, and trunk are assessed separately and then combined using weighting based on the surface area represented by each area (head = 0.1, upper extremities = 0.2, trunk = 0.3, and lower extremities = 0.4). The degree of erythema, induration, and scale in each area is judged on a 0 to 4 scale, the sum of which represents disease severity. The area of involvement of each area is graded from 0 to 6, depending on the estimated percentage of lesional area (0 = 0%, 1 = 1% to 9%, 2 = 10% to 29%, 3 = 30% to 49%, 4 = 50% to 69%, 5 = 70% to 89%, and 6 = 90% to 100%). These body scores are multiplied by the disease severity score and the weighting for each body area, yielding a score between 0 and 72. The PASI score will be program-generated.

Further practical details help the assessment: (1) the neck is assessed as part of the head; (2) the axillae and groin are assessed as part of the trunk; (3) the buttocks are assessed as part of the lower limbs; (4) when scoring the severity of erythema, scales should not be removed.

